5.2 Variables Used for Stratification of Randomization

At Visit 2, subjects will be randomized in blocks to double-blind treatment to either risankizumab 150 mg or placebo in a 4:1 ratio. Randomization will be stratified with respect to weight (≤ 100 kg vs. > 100 kg) and prior exposure to TNF antagonists (0 vs. ≥ 1).

Subjects originally randomized to risankizumab 150 mg (Arm 1) who are responders at Week 16 will be re-randomized at Week 28 in a 1:2 ratio to either risankizumab 150 mg or placebo. Re-randomization will also be stratified with respect to weight (≤ 100 kg vs. > 100 kg) and prior exposure to TNF antagonists (0 vs. ≥ 1).

6.0 Analysis Conventions

Definition of Baseline

The last non-missing measure collected on or before the date of the first dose of study drug injection will be used as Baseline for summary of demographics and disease characteristics, efficacy analyses, and safety analyses in each period, with the exception that:

- The last evaluation on or prior to the first dose date of risankizumab will be used for the safety analyses for Safety_ARM2 and ALL_RZB populations.
- For all vital sign assessments, only assessments prior to first dose time will be considered, since vital signs are to be assessed both pre- and post-dose in some visits.

For subjects who are randomized but do not take any study drug during the study, the last non-missing measurement collected on or before the date of randomization will be used as Baseline.

Definition of Final Observation (Applicable to Safety Analyses)

Final observation for the Part A1 is defined as:

- The last non-missing observation collected within 105 days following the last dose of study drug in Part A1, for subjects who were not dosed in Part A2.
- The last non-missing observation collected on or before the first dose date of study drug on or after Week 16 and within 105 days following the last dose of study drug in Part A1, for subjects who were dosed in Part A2. For vital sign assessments, only assessments prior to the first dose of study drug injection in Part A2 will be included in the analysis for Part A1.

Final observation for the Part A2 is defined as:

- The last non-missing observation collected within 105 days following the Week 16 dose of study drug in Part A2, for subjects who were not dosed in Part B.
- The last non-missing observation collected on or before the first dose date of Part B, or within 105 days following the last dose of study drug in Part A2, whichever comes first, for subjects who were dosed in Part B. For vital sign assessments, only assessments prior to the first dose of study drug injection in Part B will be included in the analysis for Part A2.

Final observation in Part B is defined as the last non-missing observation collected within 105 days following the last dose of study drug, and on or prior to the date first dose of retreatment with risankizumab for relapsed subjects, with the following exception:

For vital sign assessments, only assessments prior to the first dose of retreatment will be included in the analysis for Part B.

Final observation in the retreatment period is defined as the last non-missing observation collected within 105 days after the last dose of retreatment with risankizumab.

Final observation in the entire study is defined as the last non-missing observation collected within 105 days after the last dose of study drug.

Definition of Rx Days (Days Relative to the Date of First Dose of Study Drug)

Rx days are calculated for each time point relative to the date of first dose of study drug. They are defined as the number of days between the day of the first dose of study drug and the specific time point. Rx days are negative values when the time point of interest is prior to the first study drug dose day. Rx days are positive values when the time point of interest is on or after the first study drug dose day. The day of the first dose of study drug is defined as Rx Day 1, while the day prior to the first study drug dose is defined as Rx Day –1 (there is no Rx Day 0).

For analysis in each Part (A1, A2, or B), the Rx Day is calculated relative to the first dose of study drug in the specific study Part. For analysis across Part A2 and Part B, the Rx days are calculated relative to the date of first dose of risankizumab injection in Part A2.

Definition of Analysis Windows

All time points and corresponding time windows are defined based on Rx Days.

For efficacy analyses, local tolerability, ECG, laboratory parameters, and vital sign variables, analysis windows are constructed using the following algorithm:

- Determine the nominal Rx day for each visit (e.g., Week 4 [4 weeks after Baseline visit] equals Rx Day 29).
- In order to include all post baseline data, the first post-baseline interval starts on the first day after the first dose of study drug (Rx Day 2).
- Determine the window around a specific nominal Rx day by adding or subtracting half of the interval between adjacent visits (e.g., days between Week 2 and Week 4 is 14). The threshold between adjacent visits is determined by splitting the interval evenly between the visits. If the resulting split is between Rx days, then the threshold is determined as the midpoint between the adjacent visits. If the resulting split is on an Rx day, then the threshold is determined as being between that Rx day and the Rx day prior to it (e.g., the split between Week 2 and Week 4 would be between Rx Days 22 and 23).
- If more than one assessment is included in a time window the assessment closest to the nominal day will be used. If there are two observations equidistant to the nominal day, the one after the nominal day will be used in analyses. If more than one assessment is included on the same day, then the worst assessment on that day will be used in analyses, except those specified in Section 11.0.

The protocol specified visits and corresponding time windows used in the efficacy analyses, local tolerability, ECG, laboratory parameters, and vital sign variables, are

presented in the following Table 2, Table 3, Table 4, Table 5, Table 6, Table 7, Table 8, Table 9, Table 10, Table 11, Table 12, Table 13, Table 14, Table 15 and Table 16.

Table 2. Visit Windows for Analysis of PASI, sPGA, Local Tolerability, and Vital Signs in Part A1 (ITT_A1/PP_A1/Safety_A1 Populations)

Window Label	Target Day	Interval
Baseline	1	$\leq 1^a$
Week 4	29	[2, 43]
Week 8	57	[44, 71]
Week 12	85	[72, 99]
Week 16	113	[100, 127 ^b]

Rx Day calculated relative to first dose date of study drug. For subjects randomized but not dosed, Rx Day calculated relative to Randomization.

- a. There is no baseline for local tolerability measurements. If time is collected in vital signs, restrict to records prior to the first dose of study drug.
- b. The minimum of upper bound and first dose date of study drug on or after Week 16 (and within 105 days of last dose for safety analyses). If time is collected in vital signs, restrict to records prior to the first dose of study drug on or after Week 16.

Table 3. Visit Windows for Analysis of DLQI in Part A1 (ITT_A1/PP_A1 Populations)

Window Label	Target Day	Interval
Baseline	1	≤ 1
Week 12	85	[2, 99]
Week 16	113	[100, 127 ^a]

Rx Day calculated relative to first dose date of study drug. For subjects randomized but not dosed, Rx Day calculated relative to Randomization.

- a. The minimum of upper bound and first dose date of study drug on or after Week 16.

Table 4. Visit Windows for Analysis of Safety Laboratory Tests and ECG in Part A1 (Safety_A1 Population)

Window Label	Target Day	Interval
Baseline	1	≤ 1
Week 4	29	[2, 71]
Week 16	113	[72, 155 ^a]

Rx Day calculated relative to first dose date of study drug. For subjects randomized but not dosed, Rx Day calculated relative to Randomization.

a. The minimum of upper bound and first dose date of study drug on or after Week 16 (and within 105 days of last dose for safety analyses).

Table 5. Windows for Analysis of Efficacy Variables Collected Only at Week 16 After Baseline in Part A1 (ITT_A1 Population)

Window Label	Target Day	Interval
Baseline	1	≤ 1
Week 16	113	[2, 225 ^a]

Rx Day calculated relative to first dose date of study drug. For subjects randomized but not dosed, Rx Day calculated relative to Randomization.

a. The minimum of upper bound and first dose date/time on or after Week 16 study drug.

Table 6. Visit Windows for Analysis of PASI and sPGA in Part A2 (ITT_A2 Population)

Window Label	Target Day	Interval
Entry of A2	1	≤ 1
Week 20	29	[2, 43]
Week 24	57	[44, 71]
Week 28	85	[72, 99 ^a]

Rx Day calculated relative to the date of Week 16 visit.

a. The minimum of upper bound and first dose date on or after the first re-randomized dose for subjects with re-randomization or the first open label risankizumab dose for those who were not re-randomized.

Table 7. Visit Windows for Analysis of Efficacy Variables Only Collected at Week 28 in Part A2 (ITT_A2 Population)

Window Label	Target Day	Interval
Baseline	1	≤ 1
Week 28	85	[2, 169 ^a]

Rx Day calculated relative to the date of Week 16 visit.

a. The minimum of upper bound and first dose date on or after the first re-randomized dose for subjects with re-randomization or the first open label risankizumab dose for those who were not re-randomized.

Table 8. Visit Windows for Analysis of PASI and sPGA, Local Tolerability, and Vital Signs in Part B (ITT_B_R/ITT_B_NR/PP_B_R/Safety_B_R/Safety_B_NR Populations)

Window Label	Target Day	Interval
Entry of B	1	≤ 1 ^a
Week 32	29	[2, 43]
Week 36	57	[44, 71]
Week 40	85	[72, 99]
Week 44	113	[100, 127]
Week 48	141	[128, 155]
Week 52	169	[156, 190]
Week 58	211	[191, 232]
Week 64	253	[233, 274]
Week 70	295	[275, 316]
Week 76	337	[317, 358]
Week 82	379	[359, 400]
Week 88	421	[401, 442]
Week 94	463	[443, 498]
Week 104	533	[499, 568 ^b]

Rx Day calculated relative to the first dose date of study drug in Part B. For subjects re-randomized but not dosed in Part B, Rx Day calculated relative to the IRT date of Re-randomization evaluation.

a. There is no local tolerability at re-randomization and after EOT. If time is collected in vital signs, restrict to records prior to the first dose of study drug in Part B.

Table 8. Visit Windows for Analysis of PASI and sPGA, Local Tolerability, and Vital Signs in Part B (ITT_B_R/ITT_B_NR/PP_B_R/Safety_B_R/Safety_B_NR Populations) (Continued)

b. The minimum of upper bound, the first dose date of retreatment with risankizumab for relapsed subjects (except the additional analysis as in footnote a), and within 105 days of last dose of study drug for safety analyses. If time is collected in vital signs, restrict to records prior to the first dose of retreatment.

Note: For additional PASI and sPGA analysis on ITT_B_R subjects re-randomized to risankizumab to evaluate continuous treatment, evaluations after retreatment with open label risankizumab will also be included along with blinded assessments.

Table 9. Visit Windows for Analysis of Safety Laboratory Tests and ECG in Part B (Safety_B_R/Safety_B_NR Populations)

Window Label	Target Day	Interval
Entry of B	1	≤ 1
Week 40	85	[2, 127]
Week 52	169	[128, 211]
Week 64	253	[212, 295]
Week 76	337	[296, 379]
Week 88	421	[380, 477]
Week 104	533	[478, 589 ^a]

Rx Day calculated relative to the first dose date of study drug in Part B. For re-randomized subjects not dosed in Part B, Rx Day calculated relative to the IRT date of Re-randomization evaluation.

a. The minimum of upper bound and first dose date of retreatment with risankizumab for relapsed subjects (and within 105 days of last dose of study drug for safety analyses).

Table 10. Visit Windows for Analysis of Other Efficacy Endpoints Only Collected at Week 52, 76, and 104 in Part B (ITT_B_R/ITT_B_NR/PP_B_R Populations)

Window Label	Target Day	Interval
Entry of B	1	≤ 1
Week 52	169	[2, 253]
Week 76	337	[254, 435]
Week 104	533	[436, 631 ^a]

Rx Day calculated relative to the first dose date of study drug in Part B. For re-randomized subjects not dosed in Part B, Rx Day calculated relative to the IRT date of Re-randomization evaluation.

a. The minimum of upper bound and first dose date of retreatment with risankizumab for relapsed subjects.

Table 11. Visit Windows for Analysis of PASI and sPGA Across Part A2 and B (ITT_ARM2 Population)

Window Label	Target Day	Interval
Entry of A2	1	≤ 1
Week 20	29	[2, 43]
Week 24	57	[44, 71]
Week 28	85	[72, 99]
Week 32	113	[100, 127]
Week 36	141	[128, 155]
Week 40	169	[156, 183]
Week 44	197	[184, 211]
Week 48	225	[212, 239]
Week 52	253	[240, 274]
Week 58	295	[275, 316]
Week 64	337	[317, 358]
Week 70	379	[359, 400]
Week 76	421	[401, 442]
Week 82	463	[443, 484]
Week 88	505	[485, 526]
Week 94	547	[527, 582]
Week 104	617	[583, 652]

Rx Day calculated relative to first dose date of risankizumab.

Table 12. Visit Windows for Analysis of Other Efficacy Endpoints Collected at Week 28, 52, 76, and 104 in Part A2 and B (ITT_ARM2 Population)

Window Label	Target Day	Interval
Entry of A2	1	≤ 1
Week 28	85	[2, 169]
Week 52	253	[170, 337]
Week 76	421	[338, 519]
Week 104	617	[520, 715]

Rx Day calculated relative to first dose date of risankizumab.

Table 13. Visit Windows for Analysis of PASI and sPGA During Retreatment with Risankizumab (ITT_B_PBO_RT/ITT_B_RZB_RT Populations)

Window Label	Target Day	Interval
Entry of RTS	1	≤ 1
Week 8R	57	[2, 85]
Week 16R	113	≥ 86

Rx Day calculated relative to first dose date of retreatment with risankizumab.

Table 14. Visit Windows for Analysis of Other Efficacy Variables Only Collected at EOT and EOO Visits During Retreatment with Risankizumab (ITT_B_PBO_RT/ITT_B_RZB_RT Populations)

Window Label	Target Day	Interval
Entry of RTS	1	≤ 1
Week 16R	113	≥ 2

Rx Day calculated relative to first dose date of retreatment with risankizumab.

Table 15. Visit Windows for Analysis of Vital Signs and Local Tolerability in the ALL_RZB Population

Window Label	Target Day	Interval
Baseline	1	$\leq 1^a$
Week 4	29	[2, 43]
Week 8	57	[44, 71]
Week 12	85	[72, 99]
Week 16	113	[100, 155]
Week 28	197	[156, 239]
Week 40	281	[240, 323]
Week 52	365	[324, 407]
Week 64	449	[408, 491]
Week 76	533	[492, 575]
Week 88	617	[576, 673]
Week 104	729	[674, 785 ^b]

Rx Day calculated relative to first dose date of risankizumab.

- a. Local tolerability not measured at Baseline and at Week 104. If time is collected in vital signs, restrict to records prior to the first dose of risankizumab.
- b. The minimum of upper bound and within 105 days of last dose of risankizumab.

Table 16. Visit Windows for Analysis of Safety Laboratory Tests and ECG in the ALL_RZB Population

Window Label	Target Day	Interval
Baseline	1	≤ 1
Week 4	29	[2, 71]
Week 16	113	[72, 155]
Week 28	197	[156, 239]
Week 40	281	[240, 323]
Week 52	365	[324, 407]
Week 64	449	[408, 491]
Week 76	533	[492, 575]
Week 88	617	[576, 673]
Week 104	729	[674, 785 ^a]

Rx Day calculated relative to first dose date of risankizumab.

a. The minimum of upper bound and within 105 days of last dose of risankizumab.

The time windows specified in [Table 17](#), [Table 18](#), [Table 19](#), [Table 20](#), [Table 21](#) and [Table 22](#) will be used for the summary of study drug injections of each period.

Table 17. Visit Windows for Summary of Study Drug Injections for Part A1

Window Label	Target Day	Interval
Week 0	1	≤ 1
Week 4	29	[2, 57 ^a]

Rx Day calculated relative to the first dose date of study drug.

a. Before the first dose date of study drug on or after Week 16.

Table 18. Visit Windows for Summary of Study Drug Injections for Part A2

Window Label	Target Day	Interval
Week 16	1	≤ 1

Rx Day calculated relative to the Week 16 dose date.

Table 19. Visit Windows for Summary of Study Drug Injections for Part B

Window Label	Target Day	Interval
Week 28	1	≤ 1
Week 40	85	[2, 127]
Week 52	169	[128, 211]
Week 64	253	[212, 295]
Week 76	337	[296, 379]
Week 88	421	[380, 463 ^a]

Rx Day calculated relative to the first dose date of study drug in Part B.

a. Before retreatment.

Table 20. Visit Windows for Summary of Study Drug Injections for Subjects Retreated with Risankizumab for Relapse from Week 32 Through Week 70 (Inclusive)

Window Label	Target Day	Interval
Week 0	1	≤ 1
Week 4R	29	[2, 71]
Week 16R	113	[72, 155]

Rx Day calculated relative to the first dose date of retreatment.

Table 21. Visit Windows for Summary of Study Drug Injections for Subjects Retreated with Risankizumab for Relapse from Week 70 Through Week 82 (Inclusive)

Window Label	Target Day	Interval
Week 0	1	≤ 1
Week 4R	29	[2, 57]

Rx Day calculated relative to the first dose date of retreatment.

Table 22. Visit Windows for Summary of Study Drug Injections for Subjects Retreated with Risankizumab for Relapse After Week 82

Window Label	Target Day	Interval
Entry of retreatment	1	≤ 1

Rx Day calculated relative to the first dose date of retreatment.

Definition of Missing Data Imputation

No global imputation is taking place at the database level. Efficacy related imputations are outlined in Section 10.0. There is no imputation for missing values in the safety analyses.

Rounding of Numeric Results

Rounding will be performed for presentation of results. No rounding will be performed before or during analyses. The ROUND function of SAS will be used to round results.

When dichotomizing continuous variables, associated continuous variables will be rounded to 9 decimal points before applying the cutoff point to determine the response status (for example, percent change from baseline in PASI score will be rounded to 9 decimal places before comparing to 90%).

The mean and median will be rounded for presentation to 1 decimal more than the data entered into the database. The standard deviation will be rounded to 2 decimal places more than the data entered into the database. The minimum and maximum values will be presented as entered into the database.

Probabilities will be rounded to 3 decimal places before assignment of statistical significance and will be presented in rounded format. Probabilities that round to zero or are reported by SAS as zero will be presented as "< 0.001." Probabilities that round to 1 or are reported by SAS as 1 will be presented as "> 0.999."

7.0 Demographics, Baseline Characteristics, Medical History, and Previous/Concomitant Medications

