24. Patients should be closely monitored for signs and symptoms of hypersensitivity reactions for approximately 2 hours after the last injection at Visit 2 and for approximately one hour after the last injection at all other visits where drug is administered. Hypersensitivity reactions should be treated according to medical standards.

FLOW CHART 2 FOR RELAPSED AND RE-TREATED PATIENTS FROM WEEK 32 THROUGH WEEK 70

Relapse Visit	Re-Treatment				Follow-up #1		Follow-up	
	R1	R2	R3	R4	R5 (EOT)	EOT+ 6wks	EOT+ 16wks	
Weeks of Re-Treatment		4	8	12	16			
Day of Re-Treatment	1	28	56	84	112	154	224	
Visit window (days)		±3	±7	±7	±7	±7	±7	
Weight, waist circumference ⁴	X						X	
Vitals	X	X	X	X	X		X	
Physical examination ²	Xc	Xt	Xt	Xt	Xc	Xt	Xc	
12 lead-ECG	X	X			X		X	
Safety laboratory testing ⁵	X	X			X		X	
Adverse events	X	X	X	X	X	X	X	
Concomitant therapy	X	X	X	X	X	X	X	
Infection Testing ¹¹	X ¹¹	Xu	Xu				Xu	
Pregnancy testing ¹		X	X				X	
Contact IRT	X						X	
Local tolerability assessment	X	X	X	X				
Blood sampling for PK	X ⁷	X ⁷			X ⁷		X	
ADA assessment sampling	X ⁷	X ⁷			X ⁷		X	
Biomarker sampling ⁸	X	X			X		X	
PASI, sPGA	X	X	X	X	X	X	X	
HAQ-DI, Pain VAS/PtGA	X				X		X	
VAS ³								
TJC/SJC, DAS28 ⁹	X				X		X	
Administer trial drug ¹²	X		X(load)		X			
Termination of trial drug					X		X	
Trial completion							X	
Open label extension ⁶							X	
Vital status ¹⁰							X	

Flow Chart 2 Footnotes

1. Pregnancy Testing: X= onsite urine testing. Serum pregnancy done as a reflex if urine test is positive.
2. Physical exams: T = targeted, C = complete. Refer to [Section 5.3.1](#) for details
3. PRO= Patient Reported Outcomes are performed electronically at clinic visits and completed by patients in a quiet place prior to any other visit procedure. The order will be as follows (see also [Appendix 10.6](#) and [Appendix 10.7](#)):
 - a) HAQ-DI [for psoriatic arthritis patients at selected sites]
 - b) Pain VAS [for psoriatic arthritis patients at selected sites]
 - c) Patient Global Assessment (PtGA) VAS [for psoriatic arthritis patients at selected sites]
4. For detailed instruction how to measure waist circumference [see Section 5.3.1.1](#) of the protocol
5. Blood samples should be taken after patient has fasted for at least 8 hours prior (except screening visit). If not fasted mark on laboratory requisition.

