5.1.3 Further Endpoints

The further endpoints are as follows:

- Achievement of PASI 50 at all visits collected
- Achievement of PASI 75 at all visits collected
- Achievement of PASI 90 at all visits collected
- Achievement of PASI 100 at all visits collected
- Time until the first achievement of PASI 50, PASI 75, PASI 90, and PASI 100

- Time until loss of PASI 50, PASI 75, PASI 90, and PASI 100 response for patients re-randomised at Week 28
- Change and percent change from baseline in PASI at all visits collected
- Absolute PASI of < 3 at all visits collected
- Achievement of an sPGA score of clear or almost clear at all visits collected
- Achievement of an sPGA score of clear at all visits collected
- Time until the first achievement of sPGA of 0 or 1
- Time until loss of sPGA of 0 or 1 response for patients re-randomised at Week 28
- Time until sPGA score of ≥ 3 (relapse) for patients re-randomised at Week 28
- Change from baseline in DLQI at all visits collected
- Achievement of a DLQI score of 0 or 1 at all visits collected
- Achievement of a reduction of 5 or more points from baseline in DLQI score at all visits collected
- Change from baseline in HAQ-DI at all visits collected, in patients selected for PsA assessment.
- Change and percent change from baseline on patient Pain VAS
- Change and percent change from baseline on patient Global Assessment VAS
- Change from baseline in Swollen or Tender Joint Count (28 joints) at all visits collected in patients selected for PsA assessment.
- Change from baseline in DAS28 at all visits collected in patients selected for PsA assessment.
- Change and percent change from baseline in Nail Psoriasis Severity Index (NAPSI) at all visits collected
- Change and percent change from baseline in Palmoplantar Psoriasis Severity Index (PPASI) at all visits collected
- Change and percent change from baseline in Psoriasis Scalp Severity Index (PSSI) at all visits collected
- Change of metabolic risk factors from baseline (waist circumference, body weight, HOMA-index)

See the Flow Chart for when the above measures are collected. The above endpoints will be analyzed, where appropriate, for re-randomized subjects after receiving open-label study drug for retreatment (Flow Chart 2 and 3).

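### SAP Table 13 leaves the Week 16R retreatment window open-ended, so when that visit is missing a late Week 12 or follow-up value is reported as Week 16R

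*SAP*

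**What the plan says.** Protocol Flow Chart 2 covers patients who relapse from Week 32 through Week 70. Its visit row reads "Day of Re-Treatment 1 28 56 84 112 154 224", and its efficacy row, "PASI, sPGA X X X X X X X", marks all seven visits. PASI and sPGA are therefore collected at retreatment Weeks 4, 8, 12 and 16 and at both follow-up visits.

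SAP 6.0 builds windows from nominal visit days: "The threshold between adjacent visits is determined by splitting the interval evenly between the visits". Within a window the assessment nearest the nominal day is used, and a tie goes to the later one. For retreatment, "Table 13. Visit Windows for Analysis of PASI and sPGA During Retreatment with Risankizumab (ITT_B_PBO_RT/ITT_B_RZB_RT Populations" lists Week 8R with interval [2, 85] and then "Week 16R 113 ≥ 86", with no upper bound and no capping footnote. "Table 14. Visit Windows for Analysis of Other Efficacy Variables Only Collected at EOT and EOO Visits During Retreatment with Risankizumab" has the same open end, starting at Day 2.

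SAP 10.1.4 treats a patient with no evaluation in a window as a non-responder, unless the patient responded both before and after that window. Protocol 5.1.3 extends its list of further endpoints to retreated patients: "The above endpoints will be analyzed, where appropriate, for re-randomized subjects after receiving open-label study drug for retreatment (Flow Chart 2 and 3".

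**The concern.** A visit window decides which value carries a visit's name and when a visit counts as missing. With no upper limit on Week 16R, any later assessment can fill it, including one taken weeks after the last retreatment dose. The imputation rule is then bypassed. Its before-and-after exception cannot apply either, because no observation can lie after a window that never ends.

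The other efficacy tables set a limit: Week 16 in Table 2 ends on Day 127 and Week 104 in Table 8 on Day 568. Table 20 bounds Week 16R for injections at [72, 155]. Only Tables 13 and 14 are left open.

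Response to retreatment after relapse is a stated aim (Protocol 2.2, SAP 4.1). The figure readers will look for is the Week 16R response rate, and its label should describe what was measured.

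**Working it through.** **Inputs.** Flow Chart 2 days 28, 56, 84, 112, 154 and 224 become Rx Days 29, 57, 85, 113, 155 and 225, because the SAP counts the first dose as Day 1 and Week 4 as Day 29. The visit window is ±3 days at Week 4 and ±7 days afterwards. The midpoint day goes to the earlier window, as it does throughout the SAP tables.

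**Reproducing the plan's figures.** For Table 2: (29+57)/2 = 43, (57+85)/2 = 71, (85+113)/2 = 99, which match. For Table 13 with only Days 57 and 113 as targets: (57+113)/2 = 85, giving [2, 85] and Day 86 onward. The 85/86 split is therefore correct for the two chosen targets. The missing upper limit does not follow from the rule, because a next PASI/sPGA visit exists: (113+155)/2 = 134.

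**The rule on every Flow Chart 2 visit.** Week 4R [2, 43]; Week 8R [44, 71]; Week 12R [72, 99]; Week 16R [100, 134]; first follow-up [135, 190], since (155+225)/2 = 190; second follow-up from Day 191.

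**Which value becomes Week 16R** (nominal days unless stated):

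| Situation | Table 13 | With [100, 134] |
|---|---|---|
| All visits attended | Day 113 | Day 113 |
| Week 16 missing, Week 12 on Day 85 | Day 155 | none, so NRI |
| Week 16 missing, Week 12 on Day 86 | Day 86 (27 days from target, against 42 for Day 155) | none, so NRI |
| Week 16 and first follow-up missing, Week 12 on Day 85 | Day 225 | none, so NRI |
| Leaves the trial after the Week 4 dose; final follow-up 16 weeks later (29+112) | Day 141 | none, so NRI |

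Days 155 and 225 are 42 and 112 days (6 and 16 weeks) after the planned last dose on Day 113. A permitted Week 12 visit spans Days 78 to 92, and 7 of those 15 days fall on Day 86 or later.

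Week 8R has a smaller version of the problem. If the Week 8 visit is missing, Days 29 and 85 are both 28 days from Day 57, and the tie rule reports the Week 12 value as Week 8R.

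**Size.** Let m be the share of retreated patients without a Week 16 value and q the share of those whose status differs from what NRI would assign. The largest shift is m × q, reached if all reclassifications go one way. Neither figure is in the documents; the ranges are assumed.

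- Low: 0.02 × 0.10 = 0.2 points
- Middle: 0.05 × 0.30 = 1.5 points
- High: 0.10 × 0.60 = 6.0 points

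**The case against.** The defence is substantial, and most of it stands.

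- **The midpoint rule was applied, to fewer visits.** The boundary between the two windows reproduces exactly. Using a subset of collected visits is also done in Table 15 for vital signs. Only the missing upper limit departs from the rule.
- **Attended visits are safe.** A Week 16 visit inside its window is within 7 days of target. The latest permitted Week 12 visit (Day 92) is 21 days away and the earliest first follow-up (Day 148) is 35. A reader might infer that follow-up values displace observed Week 16 values; the nearest-day rule prevents that.
- **Flow Chart 3 patients.** They have no Week 16 visit, and their last follow-up falls near Day 141, so a reader might infer that they contaminate Week 16R by design. SAP 5.1 limits both retreatment populations to patients with the opportunity for a retreatment Week 16 assessment, and its natural reading excludes them. The exclusion is implied rather than stated.
- **Week 4 and Week 12 data.** A reader might call these lost. They have no estimate of their own, but they sit inside the existing windows and can stand in for a missing target visit. Protocol 5.1.3 asks for retreatment analyses only where appropriate, so separate windows are an improvement rather than an obligation.
- **A larger bias.** Assuming 5% missing and 80% of them responding gives 0.05 × 0.80 = 4 points of overstatement. That treats every missed visit as a failure under NRI and ignores the before-and-after exception, which already credits patients responding on both sides of the gap if follow-up counts as the same analysis period.

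What the defence does not answer is the open end itself, and what is reported when the Week 16 visit is missing.

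**Conclusion.** The point holds in limited form. When the Week 16 retreatment visit is missing, Table 13 substitutes a Week 12 value (Day 86 or later) or a follow-up value and calls it Week 16R, so the stated missing-data rule does not operate. This follows from the text without any assumption.

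The effect on the reported rate is probably small: about 0.2 to 6 points under the assumed 2-10% missing and 10-60% reclassified. The direction is not fixed. A follow-up response can replace an imputed failure, and a follow-up non-response can replace a success that the exception would have imputed.

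The retreatment endpoints are descriptive, within single-arm populations, with no alpha attached. A reader might worry about the confirmatory results, but the Week 16, 52 and 104 tests do not use Table 13.

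**What to change.** - **Table 13.** Cap Week 16R at Day 134. With Week 4R [2, 43], Week 8R [44, 71] and Week 12R [72, 99] added, Week 16R becomes [100, 134]. If only 8R and 16R are kept, use [2, 85] and [86, 134]; this keeps follow-up out but still lets a late Week 12 value stand in for Week 16R.
- **Follow-up.** Give the two follow-up visits their own windows: [135, 190] and Day 191 onward. State whether they belong to the same analysis period for the before-and-after exception.
- **Table 14.** Put a matching upper bound of Day 134 on Week 16R. The midpoint rule on those variables' own visits would give (113+225)/2 = 169, which excludes Day 225 but would still admit a Day 141 follow-up after early termination.
- **SAP 5.1.** Say explicitly that patients with no scheduled retreatment Week 16 visit, meaning Flow Chart 3 and relapse after Week 82, are outside the retreatment populations. For relapse after Week 82 the cap cannot do this, because their final follow-up falls at Day 1+112 = 113, exactly on target.

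The cost is two revised tables and a few clarifying sentences, with no new data. A few patients without a Week 16 retreatment value will be handled by NRI, so the reported rate may change slightly.
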